that incisions are covered with a postsurgical cover dressing, for up to a period of 48 hours, to help control postoperative bleeding, absorb exudate, provide mechanical protection, help to reduce edema and provide protection from exogenous sources (Mangram *et al* 1999). Multiple patient comorbidities, environmental factors and the type and length of surgery may elevate certain groups of patients into a higher level of risk of developing a post-surgical complication: calling for a higher degree of vigilance and postsurgical intervention. Surgical complications include; wound dehiscence, infection (deep or superficial), hematomas, seromas, tissue necrosis and delayed incision healing. Complication rates can range from 19% in patients requiring open reduction and internal fixation (ORIF) of tibial plateau, pilon and calcaneus fractures (Stannard *et al* 2011) up to 50% in high energy trauma wounds (Stannard *et al* 2006). These complications can have a high degree of morbidity for the patient and further sequelae may result in additional surgical procedures or revisions, a lower functional status for the patient, an increased in length of hospital stay (LOS) and a higher cost for the healthcare provider.

Traditional NPWT has been shown to be an effective adjunct therapy in the treatment of acute and chronic wounds, but the emergence of incisional NPWT (iNPWT) and supporting evidence is growing momentum. *In vitro* studies have shown that iNPWT may help to improve the stimulation of blood flow, help manage exudate, help to reduce edema, provide a mechanical and “splinting” effect on the incision and provide mechanical protection from the environment. Its impact on the prevention or reduction of post-surgical incision complications is still in its infancy, but recent studies pioneered by Stannard *et al* (Stannard 2011) have been encouraging and have demonstrated a statistically significant reduction in infection and dehiscence in patients considered as high-risk following severe skeletal trauma.

The aim of this study is to assess the prevention of incision healing complications in patients undergoing KA and THA treated with either Single-Use Incisional NPWT compared to standard of care dressings.

PRIMARY OBJECTIVE

Compare PICO wound dressing to current MOI standard of care for postoperative incision management in Knee Arthroplasty (KA) or Total Hip Arthroplasty (THA) patients.

Outcome Measures:

- Primary: Incision appearance at 1, 2 and 5 weeks postop
- VAS (Incision Healing Assessment Form) 0-10 continuous, based on standardized digital image (1 week) and exam (2 and 5 weeks). The VAS can be completed by the PI, any of the sub-investigators, or any properly trained physicians or RN associated with the project. If the VAS is completed based on an incisional photo, study staff will collect the exact date the photo was taken.
- If the subject will not be returning 2 weeks postoperatively as standard of care, they will be asked to take another standardized digital image at 2 weeks, and the 2 week follow-up will be done over the phone.

SECONDARY OBJECTIVES

To assess complications between patients treated with either PICO or standard care dressings. **Outcome Measures:**

- Secondary: Daily phone calls for first week; follow-up appointments
 - Drainage amount
 - User-friendliness for patient
 - Complications
 - Return to OR
 - Need for antibiotics

Data Analysis:

- Compare TOTAL PICO vs. SOC incision appearance VAS and drainage amount using t-Test
- Compare Primary JA (joint arthroplasty) PICO vs. SOC incision appearance VAS and drainage amount using t-Test
- Compare Revision JA PICO vs. SOC incision appearance VAS and drainage amount using t-Test
- Compare TOTAL PICO vs. SOC for all other outcome measures using chi-square based on number in each category
- Compare Primary JA PICO vs. SOC for all other outcome measures using chi-square based on number in each category
- Compare Revision TJA PICO vs. SOC for all other outcome measures using chi-square based on number in each category
- Post-hoc assessment of risk factors – ASA level, surgeon, BMI

EVALUATION DESIGN

The study will comprise a prospective, open labeled, single-centre study to determine the efficacy of a Single-Use Negative Pressure Wound Therapy (NPWT) System (PICO) in the prevention of postsurgical incision healing complications in patients undergoing KA and THA. The study will be comparative and randomized according to a pre-determined randomization schedule. The study will be open-labeled due to the physical appearance of both the investigational product and standard dressings, which will be impossible to blind to both the investigator and/or patient. Patients will be stratified according to the type of surgical procedure (KA/THA) and primary or revision procedure. Patients will be followed up for a period of 5 weeks, to determine if there are any latent problems with infection or dehiscence.

PICO

IRB Project # 1208434

Version 8

24MAR2016

NUMBER OF PATIENTS

1000 patients will be enrolled into the evaluation.

INCLUSION CRITERIA

- 1 – Patient ≥ 18 years old
- 2 - Male or non-pregnant females
- 3 – Patient is scheduled to have a surgical procedure for Knee Arthroplasty (either total knee arthroplasty or unicompartmental knee) or Total Hip Arthroplasty. May be Primary or Revision Procedure.
- 4 - The patient is able to understand the trial and is willing to consent to the trial

EXCLUSION CRITERIA

- 1 – Patients who in the opinion of the investigator may not complete the study for any reason
- 2 - Patients with a known history of poor compliance with medical treatment
- 3 - Patients who have participated in this trial previously and who were withdrawn
- 4 - Patients with known allergies to product components (silicone adhesives and polyurethane films (direct contact with wound), acrylic adhesives (direct contact with skin), polyethylene fabrics and super-absorbent powders (polyacrylates) (within the dressing)
- 5 – Patients not capable of obtaining a standardized digital picture and submitting it to the site.

ASSIGNING PATIENTS TO TREATMENT

Patients who meet all the inclusion criteria will be randomized to treatment according to a pre-determined randomization schedule. Randomization method will be [1:1](#), PICO versus standard postsurgical dressings, taken from a pre-assigned randomization table. The patient will be randomized to the application of either PICO or standard postsurgical dressings. If a patient is having a bilateral procedure, they will receive the same dressing treatment on both sides.

TREATMENT REGIME

Patients will be assessed against the eligibility criteria to determine their suitability for inclusion in the study.

Pre-Trial	
Investigator discusses study with the patient and provides the patient with a Patient Consent Form
 
Patient provides written consent to participate in the study
 
Patient functionality and QoL (quality of life) assessment (SF12)

Day 0	
Patient provides written consent to participate in the study (if not done prior to day 0)
 
Complete eligibility checklist, relevant medical history and concomitant medication
 
Patient functionality and QoL (quality of life) assessment (SF12) (*if not done at Pre-Trial visit)
 
ASA level
 
BMI
 
Operative procedure (KA or THA)
 
Incision assessment following procedure
 
First dressing application

Days 1-7 (following surgery)	
Daily communication with the subject (in person or phone contact) to collect the following information:
 
○ Drainage amount○ User-friendliness for subject (including ease of use and subject's opinion of the noise associated with the PICO device.○ Assessment of Complications○ Assessment of return to OR○ Assessment of need for antibiotics

	
*On the days within this window that fall on a weekend or holiday, the subject will not be contacted, but rather asked for a summary of this information on the next business day. If the subject is unreachable despite the site's best effort for one or a number of the days in this window, the subject will be asked to give a summary of the "missed" days.

Day 7 (1 week postoperative, +/- 3 days)	
Incision appearance: Standard digital photo of the incision (taken by the subject, family member, friend, or caregiver). Subject will submit this photo to the site.
 
VAS (Incision Healing Assessment Form) will be completed based on photo of incision.

Day 14 (+/- 7 days)	
Incision appearance: Physician exam; VAS (Incision Healing Assessment Form); Drainage amount; Assessment of complications; Assessment of return to OR; Assessment of need for antibiotics.
 
(If the subject will not be returning 2 weeks postoperatively as standard of care, they will be asked to take another standardized digital image at 2 weeks, and the 2 week follow-up will be done over the phone.)

Day 35 (+/-14 days)	
Incision appearance: Physician exam; VAS (Incision Healing Assessment Form); Drainage amount; Assessment of complications; Assessment of return to OR; Assessment of need for antibiotics.
 
Functionality and Patient's QoL Assessment (SF12)

Study Completion	Reason for Study Completion

ADVERSE EVENTS

All adverse events reported spontaneously by the patient or in response to questioning or observation by the Investigator will be recorded.

ETHICS/IRB APPROVAL

Before the start of the trial the Investigator will submit the trial to the local independent Ethics Committee/Institutional Review Board (IRB) for review and approval.

PATIENT CONSENT

Before being recruited to the clinical trial, the patient must have given written informed consent to participate.

REFERENCES

2. Mangram, AJ, Horan TC et al., (1999). The Hospital Infection Control Practices Advisory Committee. Guideline for Prevention of Surgical Site Infection, 1999. Special Report. *Infection Control and Hospital Epidemiology*, Vol 20, No 4.

APPENDIX 1

Patient Risk Grading System

The index values range from 0 to 3 points and are defined by three independent and equally weighted variables. One point is scored for each of the following when present: (1) American Society of Anesthesiologists (ASA) Physical Status Classification of >2, (2) either contaminated or dirty infected wound classification, and (3) length of operation >T hours, where T is the approximate 75th percentile of the duration of the specific operation being performed.

Calculation.....(1) + (2) + (3) = RI

(1) Physical Status Classification, American Society of Anesthesiologists*

Code Patient's Preoperative Physical Status

- 1 Normally healthy patient
- 2 Patient with mild systemic disease
- 3 Patient with severe systemic disease that is not incapacitating
- 4 Patient with an incapacitating systemic disease that is a constant threat to life
- 5 Moribund patient who is not expected to survive for 24 hours with or without operation

APPENDIX 2

VAS Scale: PICO Study Incision Healing Assessment Form. Used to represent the assessment of incision healing based on in-person visual appearance, or appearance based on standard digital photograph.

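### The primary VAS is measured at three visits, but no visit, summary over visits, significance level or decision rule is named, so no single result decides the primary objective

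*Combined protocol and SAP*

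**What the plan says.** Under PRIMARY OBJECTIVE, the outcome measure is "Primary: Incision appearance at 1, 2 and 5 weeks postop". It is a VAS scored from 0 to 10, "based on standardized digital image (1 week) and exam (2 and 5 weeks". Patients who do not come back at two weeks are handled differently: "they will be asked to take another standardized digital image at 2 weeks". The table under TREATMENT REGIME confirms separate ratings at Days 7, 14 and 35.

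The Data Analysis list then gives three lines for this outcome. The first reads "Compare TOTAL PICO vs. SOC incision appearance VAS and drainage amount using t-Test". The other two repeat the same test, one within patients having a primary procedure and one within those having a revision.

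The objective itself concerns "postoperative incision management in Knee Arthroplasty (KA) or Total Hip Arthroplasty (THA) patients", that is, the whole enrolled population. EVALUATION DESIGN says that randomisation is stratified by KA/THA and by primary or revision surgery. NUMBER OF PATIENTS gives 1000 with no effect size, SD, power or significance level. ASSIGNING PATIENTS TO TREATMENT lets bilateral patients enter with the same dressing on both sides.

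None of these sections, nor the appendices, states a primary visit, a summary over visits, a repeated-measures model, a significance level or its sidedness, or a rule for several tests of the primary outcome.

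**The concern.** A two-sample t-test needs one value per patient, and the plan supplies three without saying which one, or what combination of them, is used. The main unresolved choice is the visit. TOTAL is the natural primary population given the objective, although the plan never ranks it above the two subgroups.

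The decision rule is also undefined. Success could mean significance at any visit, at all visits, at a preferred visit or on an average. These rules have very different error rates and power, and they can give opposite conclusions from the same data. If the choice is left until results are known, the visit that happens to look best can become the primary one. Pre-specification matters more here because the assessment is not blinded ("The study will be open-labeled due to the physical appearance of both the investigational product and standard dressings"), although a visit can be chosen after the fact in any trial that does not name one.

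**Working it through.** There is no figure of the plan's own to reproduce: 1000 patients is its only planning number, and the inputs behind it are not given.

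**Inputs from the documents:** three visits; one TOTAL comparison by t-test; 1000 patients allocated 1:1, taken as 500 per arm with none lost.

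**Assumptions not in the documents:** two-sided 0.05 at each visit (critical value 1.96); equal correlation r between visits; one value per patient.

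**Step 1. Any visit counts, no true effect.** The risk is 1 - P(all three |Z| < 1.96).

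- r = 0: 1 - 0.95^3 = 0.143
- r = 0.5: 0.125
- r = 0.8: 0.098
- r = 0.9: 0.084

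The last three come from numerical integration over three equally correlated normal statistics. Simulated t-tests with 500 per arm gave 0.144 at r = 0 and 0.099 at r = 0.8. A correlation that decays from visit to visit gave 0.129 (adjacent-visit correlation 0.5) and 0.103 (0.8). Counting only results that favour PICO, the risk is 6.3% at r = 0.5 and 4.9% at r = 0.8, against a nominal 2.5%.

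**Step 2. How often the visit decides.** Among trials with a false-positive TOTAL result, exactly one of the three visits is significant in 83% at r = 0.5 and 62% at r = 0.8.

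**Step 3. All three visits must be significant.** With no true effect the risk is 0.05^3 = 0.01% at r = 0, 0.3% at r = 0.5 and 1.4% at r = 0.8. The cost is power. If each visit alone had 80% power (illustrative), requiring all three would give 0.8^3 = 51% at r = 0, and between 51% and 80% at positive correlations.

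**Step 4. Stratified allocation.** The plan balances arms within primary and revision surgery but analyses by an unadjusted t-test. If the strata differ in mean VAS, that test is slightly conservative. With a 0.5 SD difference (assumed), simulation with balanced strata gave an any-visit risk of about 11.3-11.6% at r = 0.5 (revision share 20%, assumed) and 9.4-9.5% at r = 0.8 (share 10%, assumed). These are a little below Step 1 but still about twice 5%.

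**Step 5. One named test.** A single named visit, or the three-visit average, has a 5.0% risk at every correlation.

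**The case against.** The strongest reply is that 10-12.5% is not a property of the plan. It needs a significance level, a correlation and, above all, a rule that any one significant visit counts, and the documents contain no such rule. Under an all-visits rule the error rate falls below 5% (Step 3). This stands: the defect is that the rule is undefined, and the inflated risk is one possible consequence. The 14% figure also stands only as a limit, because repeated ratings of the same incision are unlikely to be uncorrelated.

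Three stronger readings are tempting but not supported.

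- A reader might infer that every visit-by-population t-test counts as a primary result, which would raise the risk further. The objective covers KA and THA patients as a whole, and nothing makes the subgroup results decisive.
- A reader might infer that separate Primary JA and Revision JA tests will be used to claim that the effect differs between them. The plan lists a comparison within each group and announces no such claim.
- A reader might infer that the visit has been, or will be, picked from the results. The documents leave room for that but do not show it.

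It can also be said that a repeated-measures model is a preference, and that naming one visit is enough to control the error rate. That is fair, and the fix allows it. Finally, the text is Version 8, dated March 2016, and it does not show whether comparative data have already been examined.

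**Conclusion.** The point holds as a cheap improvement. The omission can be seen directly in PRIMARY OBJECTIVE and Data Analysis, and nothing later in the document fills it. As written, the primary comparison cannot be carried out without a choice that the plan does not make.

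If TOTAL is tested at each visit at two-sided 0.05 and any significant visit is read as success, the false-positive risk is about 10-12.5% at correlation 0.5-0.8 (14% at 0, 8% at 0.9) instead of 5%. That range is conditional on all three assumptions. It should not be quoted as the trial's actual type I error.

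**What to change.** Record the following in a dated amendment before any comparative data are examined.

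1. Name one primary test: the PICO minus SOC difference in VAS in the TOTAL population at two-sided 5%, either at one named visit or averaged over the three visits.
2. Estimate it from a model adjusted for the randomisation strata (KA/THA, primary/revision) in place of the unadjusted t-test. Use a repeated-measures model if all visits enter.
3. State how bilateral patients contribute one value each.
4. Report the other visits and the Primary JA and Revision JA results as supportive, with estimates and confidence intervals.

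No new data or patients are needed. The costs are these:

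- P-values at the other visits and in the subgroups can no longer be presented as primary results.
- An average mixes photo-based ratings (week 1 and some of week 2) with examination-based ones, and it dilutes an effect confined to one visit.
- A single visit avoids both problems but is less precise if the effect is similar across visits. With 1000 patients the 95% half-width is 1.96 x 2/sqrt(1000) = 0.124 SD. For the average it is 0.124 x sqrt((1 + 2r)/3), which is 0.101 SD at r = 0.5 and 0.115 SD at r = 0.8. The two options estimate different quantities, so the choice should rest first on which one answers the objective.

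### No visible rule keeps readers of the incision photos for the primary VAS unaware of the arm, although the photos could be routed to such a reader where the team allows

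*Combined protocol and SAP*

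**What the plan says.** The Primary Objective section gives the outcome as "Primary: Incision appearance at 1, 2 and 5 weeks postop". It is scored on a 0–10 VAS, from a photo at week 1 and from an exam at weeks 2 and 5. A patient who will not come back at week 2 has a phone follow-up instead, and "they will be asked to take another standardized digital image at 2 weeks". That this second photo is then scored is implied, since Appendix 2 says the form serves for both in-person and photographic assessment.

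On raters, the outcome section says: "The VAS can be completed by the PI, any of the sub-investigators, or any properly trained physicians or RN associated with the project". For photo-based scores it adds: "If the VAS is completed based on an incisional photo, study staff will collect the exact date the photo was taken". Under Treatment Regime, the week 1 photo is taken on the patient's side within 3 days either way of day 7, sent to the site, and scored on the named form. Exclusion criterion 5 removes "Patients not capable of obtaining a standardized digital picture and submitting it to the site", so a photo can be expected from every enrolled patient.

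Evaluation Design declares the trial open label because of the appearance of the products, "which will be impossible to blind to both the investigator and/or patient". The Data Analysis list has the entry "Compare TOTAL PICO vs. SOC incision appearance VAS and drainage amount using t-Test".

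**The concern.** Incision appearance on a VAS is a judgement, and a rater who knows which dressing was used may score one arm slightly better. At an in-person exam in this trial that is hard to avoid. A photo is different: the score is already separated from the bedside, so a rater with no knowledge of the arm could in principle give it. The plan collects the photos but does not ask for this.

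As written, the operating surgeon, or a nurse who phoned the patient during the first week, may score that patient's photo. With about 500 patients per arm, even a small consistent lean could by itself produce a significant difference on a primary time point.

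**Working it through.** **Rules that govern photo scoring.** The visible text sets a standardized image, a named form, trained raters drawn from the project team, a time window and a recorded photo date. None of these concerns knowledge of the arm. The part of the document before the background text and the Appendix 2 form itself could not be checked, so the statement is that no visible section sets a masking rule.

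**How a reader can learn the arm.** The daily contacts on days 1–7 include a question about the noise of the PICO device. The week 1 photo window is day 7 ± 3, that is, days 4–10. The two overlap on days 4–7. Nothing visible separates the person making the contacts from the person scoring the photo.

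**What the open-label reason covers.** It names the investigator and/or the patient and rests on what the products look like. It does not speak to a different rater who sees only a coded image of the incision.

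**The plan's own figure.** The sample size is 1000, randomized 1:1, so 1000 / 2 = 500 per arm. It cannot be reproduced, because alpha, power, SD, target difference and dropout are not given.

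**Illustration of size.** Assumptions not in the documents: two-sided alpha 0.05, all 500 per arm evaluable, one score per patient, SD 2, no true effect, and a constant reader lean b of 0.2 points in one direction.

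- SE = SD × √(2/n) = 2 × √(2/500) = 0.1265.
- P(significant) = Φ(b/SE − 1.96) + Φ(−b/SE − 1.96).
- Week 1 test, unmasked: b/SE = 0.2 / 0.1265 = 1.581; Φ(−0.379) + Φ(−3.541) = 0.353, or 35.3%.
- Week 1 test, all photos masked: b = 0, giving 5.0%.
- Week 1 test, half the photos masked, equally in both arms: b = 0.2 × 0.5 = 0.10; b/SE = 0.791; Φ(−1.169) + Φ(−2.751) = 0.124, or 12.4%.

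The plan does not say how the t-test uses the three visits. If it used their mean (SD of the mean assumed to be 2, all week 2 scores by exam, the same lean at each visit):

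- Nothing masked: b = (0.2 + 0.2 + 0.2) / 3 = 0.2, giving 35.3% as before.
- Week 1 masked only: b = (0 + 0.2 + 0.2) / 3 = 0.133; b/SE = 1.054; Φ(−0.906) + Φ(−3.014) = 0.184, or 18.4%.

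**Sensitivity of the unmasked week 1 figure.** With SD 1 it is 88.5%, and with SD 3 it is 18.4%. With SD 2 and 400 evaluable per arm it is 29.3%.

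**The case against.** The sponsor can fairly say that unmasked rating is a disclosed choice. The trial is declared open label, and the first raters listed are investigators, so nothing contradicts itself. That is correct, and it makes this a missed safeguard, not an inconsistency. It does not answer the point, because the reason given does not extend to a reader who sees only a photo.

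The sponsor can also question feasibility. At a single centre, the people who operate, phone and examine may overlap, and no section shows that every patient has a listed rater who did none of these. Someone must also receive, code and route photos that patients send to the site. Photos from days 4–10 may show the dressing, the device or marks on the skin, and the visible sections do not say when the dressings come off. All of this stands, so the remedy has to be worded as applying where the team allows. The photos could also reveal one arm more often than the other, so the half-masked figure, which assumes equal masking, may mislead.

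Finally, reach is limited. Scores at week 5, and at week 2 for patients who return, come from exams with the open-label patient present. The arithmetic is also generic: any fixed bias becomes significant with enough patients. Both points stand and bound the benefit. Neither removes the omission at week 1, which applies to every patient.

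**Conclusion.** The concern holds as an omission with a cheap partial remedy, and it should be fixed. Following the plan as written permits avoidable reader bias at week 1 for all patients, and at week 2 for an unstated share. Under the assumptions above (SD 2, 500 evaluable per arm, 0.2-point lean, no true effect), a week 1 test would be significant about 35% of the time instead of 5%. In a three-visit mean, masking week 1 alone would bring the rate down only to about 18%.

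Three stronger readings are tempting, and the documents do not support them:

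- A reader might infer that the VAS results will be biased in favour of PICO. The documents give no evidence that a lean exists, nor of its direction or size.
- A reader might infer that masked reading would protect the primary outcome as a whole. It reaches photo scores only, and it removes only the reader's bias, because the photo is still taken on the unmasked patient's side.
- A reader might take the 88.5% as the likely error rate. It needs an SD of 1 and a constant one-directional lean across raters, and neither is stated in the plan.

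Confidence is high for the omission and moderate for feasibility and benefit.

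**What to change.** In the VAS outcome text and the Day 7 and Day 14 rows of Treatment Regime, add:

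1. Week 1 photos, and any week 2 photos, carry the study number only. They are scored by an already listed rater who does not know the arm and who, where the existing team allows, did not operate on, contact or examine that patient.
2. Photo instructions ask for dressing and device to be out of frame where possible, without changing when any dressing is removed.
3. The reader records whether the photo revealed the arm, and this is reported by arm.
4. Each week 2 score is recorded as photo or exam, and week 2 results are reported by arm and mode. Otherwise masked photo scores would be pooled with unmasked exam scores.

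The cost is protocol wording, one tick box, one mode field, and the coding and routing of about 1000 week 1 photos plus the remote week 2 photos. These photos are already collected. Scoring is already planned at week 1 and implied at week 2, so no extra photos or reads are needed. Coordination at the site should be modest, but whether it can be absorbed without extra staff time cannot be told from the documents. The share of photos that can truly be masked is unknown, and exam-based scores remain unmasked.

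### The primary VAS is scored three times per patient but only a t-test is planned: it borrows nothing from a patient's other scores, and is biased if missingness at week 2 or 5 follows earlier scores differently by arm

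*Combined protocol and SAP*

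**What the plan says.** - Under PRIMARY OBJECTIVE the outcome is given as "Primary: Incision appearance at 1, 2 and 5 weeks postop". The score is a 0-10 VAS, taken from a photo at week 1 and from an exam at weeks 2 and 5. A second photo and a phone call stand in at week 2 when no visit is due.
- Data Analysis gives one method for this outcome: "Compare TOTAL PICO vs. SOC incision appearance VAS and drainage amount using t-Test". The same test is listed again within primary and within revision arthroplasty. No visit, average over visits, analysis set, covariate, repeated-measures model, rule for a missing VAS or sensitivity analysis is named.
- EVALUATION DESIGN says the trial is open label and stratified by KA/THA and by primary or revision procedure. The t-test uses neither factor, apart from the separate primary and revision comparisons.
- TREATMENT REGIME, Day 7, makes the week-1 score depend on the patient: "Subject will submit this photo to the site". The one rule for missed data is the recalled summary of the day 1-7 contacts, which does not cover the VAS.
- NUMBER OF PATIENTS: "1000 patients will be enrolled into the evaluation", allocated 1:1, so about 500 per arm.

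**The concern.** A two-sample t-test at week 5 can use only patients who have a week-5 score. A patient seen at weeks 1 and 2 but not at week 5 contributes nothing to that comparison, although the two scores in hand say a good deal about the third. Nor does the test use the factors on which randomisation is stratified.

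This matters most when the chance of a missing score depends on earlier healing and the dependence differs between arms. Patients healing badly may be harder to reach, or may come back more readily. Because patients and staff know the dressing, and the arms differ in device handling, that behaviour could differ by arm. The t-test would then compare differently selected groups, with no sign of it in the result. If missingness has nothing to do with healing, the loss is only of precision.

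**Working it through.** **Inputs from the documents.** Three VAS time points, a t-test, 1000 patients, 1:1. **Not in the documents, so assumed:** two-sided 5% level, results in SD units, higher score = worse healing (a labelling choice; it sets only the sign), visit correlation ρ, missing rate, and how missingness depends on earlier scores. The 1000 has no stated effect, SD or power, so there is no sample-size figure to reproduce.

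**Step 1: yardstick.** With 500 scores per arm, the difference detectable at 80% power is (1.960 + 0.842) × √(2/500) = 0.177 SD.

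**Step 2: how many patients are affected.** If each visit is missed independently with probability m, the share with at least one score missing and at least one present is 1 − (1−m)³ − m³. This is 27%, 48% and 63% for m = 10%, 20% and 30%. Each is lost to the test at the missed visit only.

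**Step 3: missingness follows the week-2 score in one arm only.** Simulation with no true effect, 500 per arm, three equally correlated normal scores, ρ = 0.4-0.8, base missing rate at week 5 of 15-25%, and log odds of missingness rising by 0.7 per SD of the week-2 score in one arm (e^0.7 ≈ 2). Results over the range:

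| Estimate of week-5 difference | Bias (SD) | False positives |
|---|---|---|
| t-test on available scores | 0.045 to 0.139 | 0.097 to 0.483 |
| Likelihood estimate using weeks 1 and 2 | within about 0.006 | not tabulated |

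The t-test range can be checked by hand. Bias = ρ × (shift in mean week-2 score among those still observed at week 5). The two ends imply shifts of 0.045/0.4 = 0.11 SD and 0.139/0.8 = 0.17 SD.

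- Low end, 15% and 17% missing: standard error √(1/425 + 1/415) = 0.069; 0.045/0.069 = 0.65; rejection probability P(Z > 1.31) + P(Z < −2.61) ≈ 0.10.
- High end, 25% and 27% missing: √(1/375 + 1/365) = 0.0735; 0.139/0.0735 = 1.89; P(Z > 0.07) ≈ 0.47.

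Against the yardstick, 0.05 to 0.14 SD is 28% to 79% of 0.177 SD. The missing rates differ by only two percentage points between arms, so a count of missing scores would hardly reveal the problem. At a 5% base missing rate the bias is 0.01 to 0.04 SD.

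**Step 4: same mechanism in both arms.** The arm means shift together. The bias in the difference is about 0 with no true effect, and at most about 0.013 SD with a true effect of 0.2 SD.

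**Step 5: missingness unrelated to healing.** Weeks 1 and 2 explain R² = 2ρ²/(1+ρ) of the week-5 variance. The model's standard error relative to the t-test's is √(1 − R²m).

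- ρ = 0.4, m = 0.15: R² = 0.229, ratio 0.983, about 2% smaller.
- ρ = 0.8, m = 0.25: R² = 0.711, ratio 0.907, about 9% smaller.

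**Step 6: missingness depends on the unseen week-5 score, one arm only.** The model keeps about 0.03-0.14 SD of bias, against 0.11-0.18 SD for the t-test. It reduces the bias but does not remove it.

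**The case against.** The strongest reply is that the bias is conditional on things the documents do not show. That stands. A reader might infer that any link between missingness and healing biases the comparison; Step 4 shows that it does so materially only when the link differs by arm. The missing rates are assumptions. The plan also limits missing scores: likely non-completers and poor compliers are excluded, a helper may take the photo, the visit windows are ±3, ±7 and ±14 days, and week 2 has a replacement photo. These reduce the number of missing scores but do not say how the remaining ones are handled.

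Four further inferences go beyond the documents.

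- That the plan prescribes separate tests at each visit. This is the natural reading, but the text names no visit; strictly, the plan is silent.
- That the week-1 and week-2 scores go unused. On the by-visit reading each is tested at its own visit; it is only not used to inform another visit.
- That the figures above apply to the week-1 photo. No VAS precedes week 1, so an argument from earlier scores reaches only weeks 2 and 5, and the simulation covers only week 5.
- That the photo exclusion, "Patients not capable of obtaining a standardized digital picture and submitting it to the site", goes unchecked before randomisation. TREATMENT REGIME has patients assessed against the eligibility criteria, with a checklist on Day 0, and this exclusion is one of those criteria.

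**Conclusion.** The point holds as a conditional weakness of the analysis. A primary outcome measured three times is given a method that cannot use a patient's other scores or adjust for the strata, and nothing is said about missing VAS. Material bias in the arm difference requires missingness that follows earlier scores differently by arm. Open-label treatment makes that plausible, but nothing in the documents establishes it. The sizes in Steps 3 to 6 are ranges under stated assumptions and not estimates for this trial. When the mechanism is shared by both arms, the case for change rests mainly on precision. The change should be made because it is cheap and, in every setting examined, the model does no worse than the t-test by more than simulation error.

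**What to change.** 1. In Data Analysis, replace the VAS t-tests with one mixed model for repeated measures on all available week 1, 2 and 5 scores: arm, visit, arm-by-visit, KA/THA and primary/revision as factors, unstructured covariance. Read the arm difference at each visit from it. For the primary-only and revision-only comparisons, fit the same model within the subgroup without the primary/revision term.
2. Report the number of missing VAS scores by arm and visit.
3. Add a sensitivity analysis for scores missing not at random, for example shifting the unobserved scores in one arm over a stated range. It is needed because the model removes the bias only when missingness is explained by observed scores (Step 6).

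Cost: analysis wording, one table and one extra analysis. No data collection changes. The price is reliance on the assumption that observed scores explain missingness, which item 3 examines.
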